Sample size for secondary endpoint body composition was calculated in relation to total body fat percentage. Based on previous exercise trials (20,50–52) the response within each treatment group was estimated to have a standard deviation of 2.1%. Thus, with 32 participants completing each study arm we will be able to detect a difference in delta body fat percentage of 1.5% between groups with a power of 0.8, assuming a two-sided α -level of 0.05. We will need 36 completers to attain a statistical power of 0.85. Sample size calculation for fat percentage was performed in relation to writing the SAP; after the intervention was started but prior to the termination of the intervention.

12 Framework

See point 8.

13 Statistical interim analyses and stopping guidance

No interim analyses were planned and no guidelines for terminating the trial early was made.

14 Timing of final analyses

Results from V1 to V3 will be analyzed when the final participant completes the trial. Analyses including V4 will be performed when the final participant has completed V4.

15 Timing of outcome assessments

Body weight is measured at week -8 (V0), -7, -6, -5, -4, -3, -2, -1, 0 (V1), 1, 2, 4, 9, 13, 17, 22, 26, 39, 46, 52 (V3) and 104 (V4).

Body composition is measured at V0, V1, V3 and V4.

See point 26 for timing of descriptive/explorative outcome assessments.

Section 4: Statistical Principles

16-18 Confidence intervals and P values

P-values and 95% confidence intervals will be presented for comparisons (between and within group) and will not be adjusted for multiplicity. 95% confidence intervals will be presented for estimated levels and will not be adjusted for multiplicity. A hierarchical testing procedure will be used to control the type 1 error for tests with predefined hypotheses (see point 8); all subsequent tests will be regarded as descriptive/explorative if a test fails to confirm a given hypothesis. All non-hypothesis-based tests are per definition of a descriptive/exploratory nature. Statistical significance will be claimed if the null hypothesis is rejected at the alpha level of 0.05 (two-sided), i.e. the P-value of the null hypothesis test is ≤ 0.05 . 95% confidence intervals will be required to support the tested hypothesis for hypothesis-based tests (see 8), and for exploratory/descriptive test on an absolute or relative scale not include 0 or 1 respectively.

19-20 Adherence and protocol deviations and Analysis populations

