Secondary outcome: Secondary outcome body composition is defined as change in total body fat percentage (measured to the nearest 0.01 % in fasted state with dual-energy X-ray absorptiometry (DXA) scans) from V1 to V3. In most exercise interventions with aerobic exercise, almost exclusively fat mass is lost whereas lean mass is close to unchanged (19–22). In weight loss studies with liraglutide, a combination of fat and lean mass is lost (31,32). The clinically relevant effect size for changes in fat percentage is not well described or investigated. However, based on the results of previous exercise interventions (20,57), a decrease in fat percentage equivalent of approximately 1.5 % seems to be physiologically relevant.

Descriptive/explorative outcomes:

Change from V1 to V3:

- Body composition (fat free mass (kg) and fat mass (kg))
- Circulating biomarkers of metabolic regulation to evaluate metabolic health (fasting and 3h AUC glucose (mmol/L and mmol/L*min) and fasting and 3h AUC insulin (pmol/L and pmol/L*min) for HOMA-IR and Matsuda index, HbA1c (mmol/mol), waist circumference (cm), systolic and diastolic blood pressure (mmHg), lipids (total cholesterol, HDL, LDL, and triglycerides (mmol/L))
- Safety (adverse events). Adverse events with an incident of $\geq 5\%$ in any treatment group and all serious adverse events will be reported by system organ class and preferred term for participants in all four treatment groups separately and for liraglutide pooled (exercise and non-exercise) and placebo pooled (exercise and non-exercise). Events will be reported as percentage of individuals experiencing an adverse event.
- Self-rated quality of life will be measured with the SF-36 questionnaire. Eight health concepts ranging from 0-100 will be scored: physical functioning, role limitations due to physical health problems, role limitations due to personal or emotional problems, energy/fatigue, emotional well-being, social functioning, pain, and general health perception.
- Peak oxygen uptake (absolute (ml/min) and relative (ml/min/kg))
- Stair test (S) and maximal isometric strength test (N)
- Use of medication (n, frequency)
- Meal related appetite response
- Determination of daily physical activity and sleep
- Systemic markers of immune-metabolism and oxidation
- Endothelial function
- Immuno-metabolic changes in the subcutaneous adipose tissue
- Gene expression profile of circulating inflammatory cells
- Bone health

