- Food preference questionnaire (LFPQ) and subjective appetite sensation
- Faecal bacterial composition
- Plasma metabolomics and proteomics
- Epigenetics of spermatozoa
- Questionnaires (TFEQ, IPAQ, G-SES, PSQI)

Outcomes measured at other time points:

- Body weight (week -7, -6, -5, -4, -3, -2, -1, 1, 2, 4, 9, 13, 17, 22, 26, 32, 39, 46 and V4)
- Number/proportion of participants that have reduced total body weight by $\geq 5\%$, $\geq 10\%$ and $\geq 15\%$ at V3 compared with V0
- Body composition (V0 and V4)
- Metabolic health (week 4, 13, 26, 39 and V4)
- Safety (adverse events) (week 1, 2, 3, 4, 9, 13, 17, 22, 26, 32, 39 and 46)
- Meal related appetite response (V0)
- Peak oxygen uptake, stair test and maximal isometric strength test (V0)
- Systemic markers of immune-metabolism and oxidation (V0)
- Endothelial function (V0)
- Immuno-metabolic changes in the subcutaneous adipose tissue (V0 and week 26)
- Gene expression profile of circulating inflammatory cells (V0)
- Bone health (V0 and V4)
- Food preference questionnaire (LFPQ) (V0 and V4) and subjective appetite sensation (V0)
- Faecal bacterial composition (V0)
- Plasma metabolomics and proteomics (V0, week 4, 13, 26, 39 and V4)
- Epigenetics of spermatozoa (V0)
- Questionnaires (SF-36, TFEQ, IPAQ, G-SES, PSQI) (V0 and V4)
- Measurement of sleep and physical activity levels (V0, week 13, 26 and V4)

27 Analysis methods

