Analyses of primary and secondary outcome (except for the pre-planned sensitivity analyses) will be performed based on the intention-to-treat (ITT) principle. All continuous endpoints/outcomes will be modelled using linear mixed effects models with the following fixed effects and interactions: Time (factorial), Treatment, Time (factorial)*Treatment, sex (female, male) and age group (<40 years, >40 years). The models will be specified with a restricted maximum likelihood estimation method, the Kenward-Roger degrees of freedom method, an unstructured covariance structure and a [repeated effect for visit random intercept on participant level](#). Model fit will be evaluated using graphical methods and if necessary, outcomes will be log-transformed. Estimated mean differences (CI95%) for changes between groups (main study effects), conditional means (CI95%), and within group changes (CI95%) will be extracted from the model. For log-transformed outcomes the results will be back-transformed and be presented as the ratio between estimated relative changes (CI95%), estimated conditional geometric means (CI95%) and within group relative changes (CI95%), respectively. Between group differences in changes will be null-hypothesis tested and presented with P-values.

The following predefined sensitivity analyses will be performed for the primary and secondary outcome; an additional ITT analysis with adjustment for initial weight loss, an ITT analysis using multiple imputation to assess effects of missing data (see also 28), and finally an analysis of per protocol completers.

The analysis of the primary and secondary outcome will be performed blinded to group allocation by a researcher ([name]) that have not been involved in the execution of the trial. The statistical and clinical/physiological implications of the results will be evaluated by the research team before un-blinding.

28 Missing data

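### The SAP lets significance be claimed at unadjusted P ≤ 0.05 for exploratory outcomes and does not exempt its omics platforms; if these are tested feature by feature, a large share of the claims could be false

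*SAP*

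**What the plan says.** Items 16-18 contain four statements that bear on this.

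- Multiplicity: "P-values and 95% confidence intervals will be presented for comparisons (between and within group) and will not be adjusted for multiplicity".
- Threshold: "Statistical significance will be claimed if the null hypothesis is rejected at the alpha level of 0.05 (two-sided"), which the SAP spells out as P ≤ 0.05.
- Extension beyond the hierarchy: 95% confidence intervals must support the hypothesis for hypothesis-based tests and, "for exploratory/descriptive test on an absolute or relative scale not include 0 or 1 respectively".
- Status: "All non-hypothesis-based tests are per definition of a descriptive/exploratory nature". Type I error control is confined to the eight hypotheses of item 8: "A hierarchical testing procedure will be used to control the type 1 error for tests with predefined hypotheses (see point 8").

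Item 26 lists the descriptive or explorative outcomes. For change from V1 to V3 they include "Gene expression profile of circulating inflammatory cells", faecal bacterial composition, plasma metabolomics and proteomics, and epigenetics of spermatozoa. The list for other time points repeats several of these, for example "Plasma metabolomics and proteomics (V0, week 4, 13, 26, 39 and V4").

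Item 27 says: "All continuous endpoints/outcomes will be modelled using linear mixed effects models". It adds that between-group differences in change are tested and given P-values. It excludes no outcome. No false discovery rate or other high-dimensional method appears anywhere in the SAP.

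**The concern.** For a limited set of scalar exploratory outcomes, unadjusted P-values that are openly labelled exploratory are a common and defensible choice. The same rule works differently on a platform that measures hundreds or thousands of features. There, a 5% per-test error rate produces a count of false claims that grows with the number of features, and that count can match or exceed the number of true findings.

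Items 16-18 go further than leaving the point open. They say when significance will be claimed, and they state the interval criterion that an exploratory test has to meet. An analyst who follows the text has licence to call each feature significant on its own unadjusted P-value. The trial's stated hypothesis includes immunometabolic health under the combined treatment (item 7), so a list of flagged metabolites, proteins, genes or taxa could be read as evidence of mechanism.

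**Working it through.** **Inputs from the SAP.** Per-test alpha is 0.05 two-sided, with no adjustment (items 16-18). There are four arms (item 9), so 4 × 3 / 2 = 6 possible pairwise contrasts. The design difference is 4 kg with SD 5.5 kg and 30 completers per arm (item 11).

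**Inputs not in the SAP.** The number of features per platform, the share truly affected and the effect sizes are all assumptions, shown as ranges.

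**The plan's own figure.** The SAP gives no figure for expected false claims. The sample size that supplies the design effect used below does reproduce: n per arm = 2 × (1.960 + 0.842)² × (5.5 / 4)² ≈ 29.7, which rounds up to the stated 30.

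**Step 1: expected false claims when no feature is affected.** Expected number = 0.05 × features × contrasts. This holds whether or not the features are correlated.

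| Assumed null features | One contrast | All six contrasts, one time point |
|---|---|---|
| 50 | 2.5 | 15 |
| 100 | 5 | 30 |
| 1,000 | 50 | 300 |
| 5,000 | 250 | 1,500 |

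The six-contrast column applies only if every pairwise comparison is tested, which the SAP does not specify for these platforms. Reaching 24 false claims takes 24 / 0.05 = 480 null features for one contrast, or 80 over six. Reaching 100 takes 2,000, or about 334 over six. With 50 independent null features, the chance of at least one false claim in a contrast is 1 − 0.95^50 = 0.92.

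**Step 2: share of claims that are false when some features are affected.** Assume 1,000 independent features, of which 50 (5%) are truly changed. Under the written rule, expected false claims are 950 × 0.05 = 47.5. True claims depend on the mean z-score of the affected features. The comparison is with Benjamini-Hochberg at 5%, by simulation.

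| Mean z of affected features | Unadjusted: false / true | False share | Benjamini-Hochberg: false / true |
|---|---|---|---|
| 4 | 47 / 49 | 49% | 2 / 41 |
| 2.82 | 48 / 40 | about 54% | 1 / 15 |
| 2 | 47 / 26 | about 65% | below 1 / 2 |

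The middle row is the trial's own design effect: 4 / 5.5 = 0.73 SD, and with 30 per arm z = 0.73 × √(30 / 2) ≈ 2.82. A mean z of 4 would need 4 / √15 ≈ 1.03 SD.

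**Step 3: is there an exemption?** Items 16-18 give the interval criterion for exploratory tests, item 26 places the platforms among the exploratory outcomes, and item 27 models all continuous outcomes. Read together, they leave the platforms inside the rule.

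**The case against.** **Scope.** The document is headed as a plan for clinical outcomes and is tied to one article on weight maintenance, body composition and health. The omics entries are single lines with no platform, unit, normalisation or summary measure, whereas the clinical exploratory outcomes carry units and derivations. They may be only an inventory of trial assessments. This is the strongest point. It makes a separate omics plan plausible, but the SAP does not mention one, and the outcomes stand in its list under its rules.

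**Feature-wise testing is not stated.** Bacterial composition or an expression profile could be analysed through diversity, module or multivariate summaries, and some of these data may not suit the model in item 27. This stands, and it is why the point is conditional.

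**Exploratory label.** Items 16-18 declare every test without a predefined hypothesis exploratory. This protects the confirmatory results fully. It does not withdraw the permission to claim significance, because the same paragraph states the criterion that exploratory tests must meet.

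**Cost of adjustment.** At the design effect, false discovery rate control at 5% drops more than 60% of the true features that the unadjusted rule would flag. This stands. Adjustment is a real trade-off in a trial of this size, and both its level and its family are matters of choice.

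**Stronger readings to avoid.** A reader might infer that false findings will appear by the dozen or hundred. The documents do not support that as a fact: no feature count or set of contrasts is given, and a targeted panel of 50 null features would yield 2.5 per contrast. A reader might also infer that the trial's type I error is compromised. It is not, since the hierarchy for the eight hypotheses is separate from these tests.

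**Conclusion.** The point holds in conditional form. As written, the SAP permits claims of significance at unadjusted P ≤ 0.05 for the omics outcomes that it lists, and nothing exempts them.

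If features are tested individually, the expected number of false claims is 5% of the null features per contrast. With 1,000 features and 5% truly affected, roughly half to two thirds of the claims would be false, depending on effect strength. These figures rest on assumed feature counts, an assumed share of affected features and, for the simulation, independence between features.

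The consequence is confined to exploratory reporting. No primary or secondary estimate, test or conclusion changes.

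**What to change.** Add one sentence to items 16-18, in either of two forms.

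1. State that metabolomics, proteomics, gene expression, faecal bacterial composition and epigenetic outcomes lie outside this SAP's significance rule and will be analysed under a separate plan.
2. State that, where features of these platforms are tested individually, significance is claimed only on a Benjamini-Hochberg adjusted value within platform and contrast, at a prespecified level (5%, for example), and that unadjusted P-values are shown as descriptive only.

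The rule for scalar exploratory outcomes can stay as it is. Neither form needs new data or touches the primary and secondary analyses. The first costs nothing here but defers the decision. The second lowers the number of true features flagged, by the amounts in the second table above. The loss is modest for strong effects and substantial at the trial's design effect, so the level should be chosen with that in view. Because unadjusted results are still displayed, only the claim of significance is lost and the data remain visible.

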The distribution of all outcomes included in baseline characteristics will be visually inspected using QQ-plots and histograms; those with a Gaussian distribution will be presented as means and standard deviations and those with a non-Gaussian distribution will be presented as medians plus 25th and 75th percentiles.

The following outcomes will be included in the baseline participant characteristics table for all participants combined at V0, all participants combined at V1 and participants divided by randomization group at V1:

- Number of participants (men/women)
- Age (years)
- Weight (kg)
- BMI (kg/m²)
- Waist circumference (cm)
- Total fat mass (kg)
- Total fat free mass (kg)
- Body fat percentage (%)
- Systolic blood pressure (mmHg)
- Diastolic blood pressure (mmHg)
- HbA1c (mmol/mol)
- Fasting glucose (mmol/L)
- Fasting insulin (pmol/L)
- Fasting C-peptide (pmol/L)
- Glucose AUC (mmol/L*min)
- Insulin AUC (pmol/L*min)
- Cholesterol: total, LDL and HDL (mmol/L)
- Triglycerides (mmol/L)
- Peak oxygen consumption (ml/min)
- Peak oxygen consumption (ml/min/kg)
- HOMA-IR (fasting insulin (pmol/L) * fasting glucose (mmol/L) / 22.5)
- Matsuda index (10000/sqrt(fasting glucose * fasting insulin * mean glucose * mean insulin))
- SF-36 (scoring of eight health concepts ranging from 0-100: physical functioning, role limitations due to physical health problems, role limitations due to personal or emotional problems, energy/fatigue, emotional well-being, social functioning, pain, and general health perception)
- ALAT (U/L)
- Amylase (U/L)
- CRP (mg/L)

Section 6: Analysis

26 Outcome definitions

Primary outcome: Primary outcome is the change in total body weight (measured to the nearest 0.1 kg) from baseline (V1) to end-of-treatment (V3). A weight difference of 2.5-4.5 % body weight, obtained with liraglutide or semaglutide compared to placebo, have been associated with beneficial cardiovascular outcomes (45,46). A weight difference of 1-5% of body weight obtained with exercise has been associated with beneficial cardiovascular disease risk factors (17,18) and prevention of diabetes (54).

Thus, a difference in delta of 3-5% of total body weight has been defined as the minimal important difference. With a study population consisting of men and women (expected mean height of 170-174 cm based on previous lifestyle trials performed in Denmark (15,55,56) and a BMI range of 32-43 kg /m², a difference of 3-5% of total body weight will correspond to 4 kg.

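### HOMA-IR is defined with insulin in pmol/L but with the divisor 22.5, which fits insulin in mU/L; the Matsuda formula states no units

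*SAP*

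**What the plan says.** The list of baseline variables in SAP item 25 contains two formulas. The first is "HOMA-IR (fasting insulin (pmol/L) * fasting glucose (mmol/L) / 22.5", with the units written inside it. The second is "Matsuda index (10000/sqrt(fasting glucose * fasting insulin * mean glucose * mean insulin", with no units. The same list gives the measured quantities as "Fasting glucose (mmol/L" and "Fasting insulin (pmol/L".

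Item 26 places both indices among the descriptive/explorative outcomes for change from V1 to V3. It lists the biomarkers as "fasting and 3h AUC glucose (mmol/L and mmol/L*min" and "fasting and 3h AUC insulin (pmol/L and pmol/L*min) for HOMA-IR and Matsuda index".

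The SAP nowhere mentions mU/L, mg/dL, a conversion factor or a conversion step.

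Item 27 analyses continuous outcomes with a linear mixed model and takes logs only where model fit calls for it. In that case, "For log-transformed outcomes the results will be back-transformed and be presented as the ratio between estimated relative changes (CI95" and intervals are reported, together with geometric means.

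**The concern.** The constants in both indices depend on the units of the inputs. The divisor 22.5 is the product of reference values of 5 mU/L insulin and 4.5 mmol/L glucose, so the index equals 1 at those values. The SAP keeps 22.5 but writes insulin in pmol/L. At 4.5 mmol/L glucose, its formula returns 1 only when insulin is 5 pmol/L, which is 5/6.945 = 0.72 to 5/6.0 = 0.83 mU/L.

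For Matsuda, 10000 goes with glucose in mg/dL and insulin in mU/L. The SAP names neither unit.

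What is at stake is the meaning of the displayed numbers. Item 25 shows both indices at V0, at V1 overall and at V1 by group. Item 24 repeats the baseline variables for completers and non-completers. Item 26 includes the indices in the V1 to V3 changes. Values on the wrong scale, labelled HOMA-IR or Matsuda, could not be compared with other studies or with published cut-offs.

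**Working it through.** The SAP states no numerical HOMA-IR or Matsuda value, so there is no figure of its own to reproduce. The check is a unit conversion.

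**Inputs from the SAP**
- HOMA-IR: insulin in pmol/L, glucose in mmol/L, divisor 22.5 (item 25).
- Matsuda: numerator 10000 over the square root of fasting glucose, fasting insulin, mean glucose and mean insulin multiplied together, units not given (item 25).
- Measured units: mmol/L and pmol/L (items 25 and 26).

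**Assumptions not in the SAP**
- 22.5 is for insulin in mU/L and glucose in mmol/L.
- 10000 is for insulin in mU/L and glucose in mg/dL.
- 1 mU/L insulin = k pmol/L, with k from 6.0 to 6.945.
- 1 mmol/L glucose = 18 mg/dL.

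**HOMA-IR**
- As written: I(pmol/L) × G / 22.5.
- Standard: (I(pmol/L) / k) × G / 22.5.
- Ratio of the two: k, that is 6.0 to 6.945.
- Example (assumed values) with 80 pmol/L and 5.5 mmol/L: as written, 80 × 5.5 / 22.5 = 19.6. Standard: 19.56 / 6.0 = 3.26, or 19.56 / 6.945 = 2.82.

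**Matsuda, if SI values are entered unconverted**
- The standard product contains two glucose terms, each multiplied by 18, and two insulin terms, each divided by k.
- Ratio of unconverted to standard: sqrt(18² / k²) = 18 / k. This is 18 / 6.0 = 3.00 or 18 / 6.945 = 2.59.
- Example (assumed values): fasting glucose 5.0 and mean glucose 7.0 mmol/L; fasting insulin 10 and mean insulin 60 mU/L.
- Standard: 10000 / sqrt(90 × 10 × 126 × 60) = 3.83.
- Unconverted, k = 6.0: 10000 / sqrt(5 × 60 × 7 × 360) = 11.5.
- Unconverted, k = 6.945: 10000 / sqrt(5 × 69.45 × 7 × 416.7) = 9.94.

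Neither ratio depends on the example values. They move in opposite directions with k: a larger k means more HOMA-IR inflation and less Matsuda inflation.

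**Effect on the analysis**
- On the untransformed scale, multiplying an outcome by a constant multiplies means, changes, differences and interval limits by that constant. Test statistics, P-values, and whether an interval excludes 0 stay the same.
- On the log scale, the constant is an added intercept. It cancels from between-group ratios and within-group relative changes, but remains in the geometric means.

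**The case against.** The strongest objection is to the Matsuda part. A reader might infer that this formula is wrong in the same way as HOMA-IR. The document does not support that. The formula carries no units and is wrong only if unconverted SI values go into it. Item 26 lists SI units for the biomarkers in connection with the index, but it names fasting and AUC values, whereas the formula uses fasting and mean values. It is therefore not an input specification. This objection stands: for Matsuda the fault is missing units, and the inflation is conditional.

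A second objection is that the meaning of both constants comes from outside the SAP. That is true, and it is stated as an assumption, with k shown as a range. The assumed conventions are part of what the named indices mean.

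A third is that the unit label may have been carried over from the fasting insulin entry in the same list, with conversion done in code. That is possible. A reader might infer that the reported values will be wrong, and the SAP cannot establish that. It establishes that unit and constant do not match as written. Correct code would then depart from the written definition, which would still need correction.

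A fourth is that little depends on the indices. This also stands. Neither appears in hypotheses 1 to 8, both lie outside the testing hierarchy of items 16-18, and the SAP applies no cut-off to either.

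**Conclusion.** The HOMA-IR definition in item 25 is wrong as written. Applied literally, it gives levels, absolute changes, absolute differences and confidence limits 6.0 to 6.9 times too high, assuming the standard definition and k = 6.0 to 6.945. If the outcome is log-transformed, geometric means carry the same factor and ratios do not.

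The Matsuda definition is incomplete because it states no units. The 2.6 to 3.0-fold inflation holds only if mmol/L and pmol/L values, the only glucose and insulin units the SAP gives, are used unconverted with 10000.

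Severity is minor. A reader might infer from a six-fold error that treatment comparisons are at risk. They are not: P-values, group ordering and log-scale ratios are unchanged, and no confirmatory hypothesis is involved. Only baseline and exploratory displays, and their comparison with other studies, are affected.

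**What to change.** In item 25:
- Define HOMA-IR = (fasting insulin in pmol/L / k) × fasting glucose in mmol/L / 22.5, and state the k that applies to the assay.
- Write the units into the Matsuda formula. Convert fasting and mean glucose to mg/dL (times 18) and fasting and mean insulin to mU/L (divided by k) before applying 10000.

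An equivalent option is to keep SI inputs and change the constants. The HOMA-IR divisor becomes 22.5 × k, which is 135 for k = 6.0 or 156.3 for k = 6.945. The Matsuda numerator becomes 10000 × k / 18, which is 3333 or 3858. The same k must be used for both indices.

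The cost is a change of SAP wording and one line of code. It needs no further patients or data and does not affect power.
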